## 7. PARTICIPANT SAFETY

### 7.1. Risks, Benefits, and Inclusion of Children

**Component analysis: Monitoring** - There is the prospect of direct benefit to the individual participants for their participation in the study. These potential benefits include the recognized benefits of being in a clinical study, including the close monitoring offered to all participants regardless of group assignment. As noted in the introduction, marked hyperglycemia and DKA occur frequently at the time of clinical diagnosis. Close monitoring of autoantibody positive individuals using an OGTT has been demonstrated to have direct clinical benefit. The presence of DKA at diagnosis is reduced from more than 25% to 3-4% when in close monitoring. For those under 5, the frequency of DKA at diagnosis is reduced by two thirds. Moreover, in the general T1D population, the mean HbA1c at diagnosis is 11%. This contrasts with a mean HbA1c of 6-8% when closely monitored, indicating less exposure to hyperglycemia. OGTTs are generally considered a minimal risk procedure, as they just involve an IV placement and the ingestion of oral glucose. Other procedures, venipuncture, laboratory tests, histories, physical examinations, and ophthalmologic examinations are likewise generally considered to be minimal risk. The monitoring aspects of this study are therefore consistent with the United States Department of Health and Human Services, Protection of Human Subjects, Subpart D, section 46.404 (research not involving greater than minimal risk) and with the Food and Drug Administration, Protection of Human Subjects, Subpart D, section 50.51 (Clinical investigations not involving greater than minimal risk).

**Component analysis: Intervention Arm - hydroxychloroquine** – The use of hydroxychloroquine offers the prospect of direct benefit. As described above in this protocol, hydroxychloroquine is a Food and Drug Administration (FDA)-approved agent for malaria as well as rheumatoid arthritis (RA) and discoid and systemic lupus erythematosus (SLE). It is widely used in clinical practice for these indications, including in pediatric populations. Efficacy in autoimmune disease has been well established in RA, SLE, antiphospholipid syndrome, and Sjögren's syndrome. Particularly relevant for this study is that hydroxychloroquine is effectively used early in the course of autoimmune disease, having been shown to slow or halt progression in palindromic rheumatism and in delaying onset of SLE in antibody positive individuals. Other beneficial actions of hydroxychloroquine have been identified with use of the drug in other autoimmune diseases, including improvement in cardiovascular risk factors, such as reduction of LDL cholesterol, thrombosis, glycemia, insulin resistance, and reduction of risk of incident diabetes mellitus in SLE and RA. Positive effects of hydroxychloroquine on beta cell function and insulin sensitivity have also been demonstrated in healthy volunteers, possibly mediated through anti-inflammatory effects. The risks of

hydroxychloroquine are thus justified by the anticipated benefit to the participants and the relation of the anticipated benefit to the risk is at least as favorable to the participants as that presented by available alternative approaches.

This research proposal in children is therefore consistent with the United States Department of Health and Human Services, Protection of Human Subjects, Subpart D, section 46.405 (research involving greater than minimal risk but presenting the prospect of direct benefit to the individual participants) and with the Food and Drug Administration, Protection of Human Subjects, Subpart D, section 50. 52 (Clinical investigations involving greater than minimal risk but presenting the prospect of direct benefit to individual participants) **for those in the hydroxychloroquine treatment arm.**

**Component analysis: Placebo Arm** - The placebo intervention has no known risks and is therefore consistent with the United States Department of Health and Human Services, Protection of Human Subjects, Subpart D, section 46.404 (research not involving greater than minimal risk) and with the Food and Drug Administration, Protection of Human Subjects, Subpart D, section 50. 51 (Clinical investigations not involving greater than minimal risk).

**Summary:** Assent of children, along with consent of both parents/legal guardians, as applicable according to country and IRB or ethics board requirements, will be obtained prior to any study procedures. This research proposal in children is consistent with the United States Department of Health and Human Services, Protection of Human Subjects, Subpart D, section 46.405 (research involving greater than minimal risk but presenting the prospect of direct benefit to the individual participants) and with the Food and Drug Administration, Protection of Human Subjects, Subpart D section 50. 52 (Clinical investigations involving greater than minimal risk but presenting the prospect of direct benefit to individual participants) for those in the active treatment group and is consistent with the United States Department of Health and Human Services, Protection of Human Subjects, Subpart D, section 46.404 (research not involving greater than minimal risk) and with the Food and Drug Administration, Protection of Human Subjects, Subpart D, section 50. 51 (Clinical investigations not involving greater than minimal risk) for those in the placebo group.

## 7.2. Expected Side Effects and Adverse Events

A full description of the adverse events linked to hydroxychloroquine is available within the prescribing information found in the medication packet insert. The descriptions below highlight the most important and/or common drug-related events and potential adverse events.

### Gastrointestinal:

Gastrointestinal side effects are common, affecting between 1-10% of users. These include nausea, diarrhea, abdominal discomfort and vomiting. These symptoms are dose-related and stop with cessation of drug. Less than 10% of those with these symptoms choose to discontinue therapy.

### Ophthalmologic:

The most important adverse effect of hydroxychloroquine is retinal toxicity. In a retrospective case-control study of 2,361 individuals who had taken hydroxychloroquine for at least 5 years, retinopathy was seen in 7.5% of users when assessed with spectral domain optical coherence tomography and 10 degree standard automated perimetry visual fields; as duration of use increases, an unknown, but

higher percentage that varies with the daily dose was seen. The risk of retinopathy was duration- and dose-dependent, and was less than 2% within 10 years in those taking 4-5 mg/kg/day. There is negligible risk when duration of therapy <6 months and it is unlikely to occur if dose is <5 mg/kg/day actual body weight (generally equivalent to 6.5 mg/kg/day ideal body weight) up to 400 mg/day. Moreover, retinopathy detected by these sensitive techniques is not equivalent to clinically apparent or significant visual effects. Despite longstanding use of hydroxychloroquine for malaria therapy in very young children, there is a dearth of information about retinopathy, suggesting its rarity. Current practice recommendation by the American Academy of Ophthalmology is annual examination after 5 years of drug exposure in those on daily doses  $\leq 5.0$  mg/kg with no major risk factors.

Dermatologic AEs (pruritus, allergic rashes, and increased skin pigmentation), neuromuscular AEs (muscle aches), and insomnia each occur 1% of the time and resolve within 1-2 weeks with continued therapy.

Cardiovascular: Hydroxychloroquine has the potential to cause QT prolongation and should not be administered with other drugs that have a potential effect on the QT interval (*see Drugs Interactions; section 7.2.4.2*). In addition, rare cases of cardiomyopathy have been reported in those over age 50 who received high doses of hydroxychloroquine over a long duration.

Thrombocytopenia and hemolysis are rare and are probably associated with high doses, other drugs, or G6PD deficiency.

There are case reports of allergic reactions (urticarial, angioedema), abnormal liver function tests, and skeletal muscle myopathy, which are reversible over time.

### **7.2.1. Immunizations**

With widespread clinical use, there is no evidence that hydroxychloroquine has an impact on the safety or efficacy of vaccines. As such, all participants will be instructed to maintain their standard clinically indicated immunization schedules. However, the mechanism of action of the drug raises the theoretical possibility that live cellular vaccines could be less effective while receiving hydroxychloroquine.

### **7.2.2. Pregnancy**

Hydroxychloroquine is widely used in pregnancy without safety concerns. However, due to the impact of pregnancy on study outcome measures and the fact that the drug is being tested for a new indication, female participants with reproductive potential will be instructed to avoid pregnancy and use birth control while on study. They will undergo urine pregnancy testing at the start of every study visit. All pregnancies that are identified during the study must be requested to be followed to conclusion and the outcome of each must be reported. The investigator should be informed immediately of any pregnancy occurring in a female participant. Monitoring of the participant should continue until the conclusion of the pregnancy. Participants who are found to be pregnant while on this study shall have treatment

withheld, but will still be followed for safety. Treatment may only be resumed when these participants are no longer pregnant or breast-feeding.

### **7.2.3. Risk of Overdose**

A number of fatalities have been reported in children following the accidental ingestion of the 4-aminoquinoline compound chloroquine, sometimes in relatively small doses. However, hydroxychloroquine is a different drug. It has less toxicity overall, and a higher therapeutic ratio.

### **7.2.4. Prohibited Medications**

Participants will be asked to consult with their study team before taking any new therapy.

#### **7.2.4.1. Drugs that may impact T1D progression or effect of Hydroxychloroquine**

Participants will be instructed not to use prednisone, other immunosuppressive agents, or chronic inhaled or nasal corticosteroids during this trial in order to prevent possible impact on progression to diabetes. They will also be instructed not to use proton pump inhibitors or antacids, which may inhibit accumulation of hydroxychloroquine in lysosomes by decreasing the pH of these organelles, and thus potentially antagonizing immunomodulating effects. However, as an intention-to-treat study, no individual will be withdrawn from analysis if this occurs.

#### **7.2.4.2. Hydroxychloroquine drug interactions**

Hydroxychloroquine has known drug interactions with therapies that are unlikely to be used by the population enrolled in this study. Upon review by the TrialNet medical monitor, participants who have a clinical indication to take these medications after enrollment may be withdrawn temporarily from study treatment while on these other medications, or permanently, but with continued monitoring and safety assessments for this trial. These medications include monoamine oxidase inhibitors, anti-arrhythmogenic drugs such as amiodarone, cyclosporine, digoxin, halofantrine, other anti-malarials, anti-epileptic drugs, praziquantel, agalsidase, CYP34A inhibitors such as cimetidine and ketoconazole (which may increase hydroxychloroquine levels), penicillamine, bosutinib, droperidol, lanthanum, laronidase, cholinesterase inhibitors, and kaolin. Hydroxychloroquine potentially prolongs the QT interval, and therefore should not be co-administered with other drugs that potentially prolong the QT interval, including SSRIs.

### **7.3. Protecting Against or Minimizing Potential Treatment Risks**

Participants who have other active serious medical problems will not be enrolled. Frequent monitoring of participants with history, physical examination, and laboratory studies will allow for early identification of adverse events. Every attempt will be made to minimize the number of venipunctures. Participants will be screened for G6PD deficiency and excluded if present.

To mitigate potential ophthalmologic risk, a fundus photograph or examination will be attempted at Baseline, and OCT and visual field examinations will be attempted annually in all participants. Participants with a successful OCT examination may continue with the study per protocol. If neither the OCT nor visual field examination can be successfully completed (e.g., in very young children), these

examinations will be re-attempted on an annual basis while the participant continues on study drug. The target dose of hydroxychloroquine will be 5.0 mg/kg/day to a maximum of 400mg. This is below the dose associated with ophthalmologic risk. Moreover, individuals who reach study endpoint (abnormal glucose tolerance) will be considered to be a non-responder and withdrawn from therapy, thus decreasing duration of exposure.

Individuals will be informed of potential impact on skin, sleep, gastrointestinal symptoms, and muscle aches. If symptoms continue or are intolerable, drug dose may be temporarily reduced or stopped, at the discretion of the investigator in consultation with the medical monitor. If signs or symptoms are consistent with infectious mononucleosis, evaluation may include measurements of EBV serology and viral load as clinically indicated.

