### **2.2.3 Safety and Tolerability of Hydroxychloroquine**

Hydroxychloroquine has been in clinical use for >60 years. It is generic and its pharmacological characteristics and safety profile have been established in pediatrics, adults, and pregnancy. It is considered a far safer drug than its close relative chloroquine. It is well tolerated, with the most common side effects being transient nausea experienced by 1-10% of patients. Few individuals stop therapy due to side effects, and 'once daily' dosing facilitates adherence. The recommended pediatric dose is 5–6.5 mg/kg once daily (max. dose 400 mg).

The most important adverse effect of hydroxychloroquine is retinal toxicity (see Section 7.2). This is correlated with dose of drug and duration of therapy. There is negligible risk for duration of therapy <6 months, and it is unlikely to occur with less than 5 years of therapy if dose is <5 mg/kg/day up to 400 mg/day. Despite longstanding use of hydroxychloroquine for malaria therapy in very young children, there is a dearth of information about retinopathy, suggesting its rarity.

In this study, hydroxychloroquine dose will be targeted at a maximum of 5.0 mg/kg/day actual body weight up to 400 mg/day and individuals will undergo annual ophthalmological exams.

Section 7.2 describes other reported adverse effects.

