### **3.9. Study Timeline**

#### **3.9.1. Study Duration**

The study has been designed to provide 83% power to detect a 50% risk reduction in the progression from Stage 1 to Stage 2 or 3 T1D using a two-sided test at the 0.05 level after six years of study duration (approximately 4 years of accrual and a minimum of 2 years of follow-up on all subjects). A total of approximately 201 participants will be allocated in a 2:1 ratio to the two groups.

The assumptions underlying the sample size are: 1) 40% two-year event rate in the placebo group for the progression from Stage 1 to Stage 2 or 3 T1D, 2) detectable hazard ratio of 0.50 (i.e., reducing the hazard rate by 50%, which here translates to 40% vs. 22.5% in the two-year event rates) in the hydroxychloroquine group, 3) a 10% or less dropout rate for a minimum of 2 years of follow-up on all participants in both groups, and 4) assumption that the distribution of time to T1D stage progression is approximately exponentially distributed. Under the above assumptions, the total target number of events that would trigger the final analysis is 80; i.e., the final analysis will be conducted once 80 events (abnormal glucose tolerance or diabetes) have been observed. If the accrual rate is 50 patients per year, with the above assumptions it is estimated that the enrollment period will last approximately 4 years, with a total study duration of approximately 6 years to provide a sufficient number of events to detect the powered detectable difference.

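### Protocol 7.3 places the 5.0 mg/kg/day target below the dose linked to eye risk, which conflicts with the risk figures in 2.2.3 and 7.2; the texts on annual eye examinations also disagree

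*Protocol*

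**What the plan says.** **Dose and risk.** Protocol 7.3 states: "The target dose of hydroxychloroquine will be 5.0 mg/kg/day to a maximum of 400mg". It follows this with: "This is below the dose associated with ophthalmologic risk". Protocol 7.2 (Ophthalmologic) describes retinopathy risk as depending on both dose and duration, and says that it "was less than 2% within 10 years in those taking 4-5 mg/kg/day". The same paragraph adds that "it is unlikely to occur if dose is <5 mg/kg/day actual body weight", with no time limit in that sentence. Protocol 2.2.3 does set one: "it is unlikely to occur with less than 5 years of therapy if dose is <5 mg/kg/day up to 400 mg/day". Protocol 4.5.1 sets dosing in 100 mg increments, with a weekly average of at most 5 mg/kg/day and a 400 mg daily maximum.

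**Duration.** Protocol 3.9.1 plans about 4 years of accrual, "with a total study duration of approximately 6 years to provide a sufficient number of events", and sets the final analysis at 80 events. Appendix 2 note 1 follows each participant until the endpoint or the end of the trial.

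**Examinations.** Protocol 2.2.3 says "individuals will undergo annual ophthalmological exams", and Appendix 2 note 7 schedules them for all participants from month 12. Protocol 7.3 says that OCT and visual fields will be attempted annually. For participants who can complete neither, it says these "examinations will be re-attempted on an annual basis while the participant continues on study drug".

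**Denominators.** The retinal hold criterion in Protocol 4.5.2 item 3 uses a percentage of all treated participants. SAP section 8 uses the total population size as the denominator for adverse event incidence.

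**The concern.** Section 7.3 is the part of the protocol that explains how treatment risk is kept down, in a trial that enrols from age 3. Its dose sentence is a flat assurance. The sections it depends on are conditional: they give a small risk in a dose band that contains the target, and they limit the reassurance by dose and, in 2.2.3, by time on therapy. An ethics board or DSMB member who reads 7.3 alone would come away with a different picture from one who reads 7.2.

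The examination texts raise a second, separate question. If some participants never complete a retinal test, no OCT or visual-field finding can come from them, yet they still enlarge the denominator. A reported retinal rate would then be lower than the rate among people actually examined, and nothing in the plan would show by how much.

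**Working it through.** **1. Is the target below the band with a stated risk?**
Section 4.5.1 caps the weekly average at 5 mg/kg/day, which is 35 mg/kg per week. Assume the largest permitted multiple of 100 mg per week, up to 2800 mg (7 x 400 mg):

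daily dose per kg = floor(35 x weight / 100) x 100 / (7 x weight)

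| Weight (kg) | Weekly dose (mg) | mg/kg/day |
|---|---|---|
| 12 (entry minimum) | 400 | 4.76 |
| 14.28 (lowest value in 12-80 kg) | 400 | 4.00 |
| 20, 40, 60, 80 | 700, 1400, 2100, 2800 | 5.00 |
| 100 | 2800 (cap) | 4.00 |

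From 12 to 80 kg every weight gives 4.00 to 5.00 mg/kg/day. That is the band to which 7.2 attaches its risk figure. At 5.00 the strict inequality in 2.2.3 and 7.2 is not met.

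**2. The plan's own design figure.**
With 80 events, 2:1 allocation and a hazard ratio of 0.50, the expected Z is sqrt(80 x 2/9) x ln 2 = 2.92. Power is Phi(2.92 - 1.96) = 0.83. The stated 83% is reproduced.

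**3. Does exposure pass 5 years?**
Inputs from Protocol 3.9.1 and 8.4: 135 on active drug, even accrual over 4 years, exponential times, 40% two-year placebo rate, 10% two-year dropout.
- Placebo hazard = -ln(0.60)/2 = 0.2554 per year. Active hazard at HR 0.50 = 0.1277.
- Dropout hazard = -ln(0.90)/2 = 0.0527.

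*Close at 6 years.* Those enrolled in the first year can pass 5 years: 135/4 = 33.75.
- HR 0.50, no dropout: 33.75 x exp(-5 x 0.1277) = 17.8
- HR 0.50, with dropout: 33.75 x exp(-5 x 0.1804) = 13.7
- No drug effect: 33.75 x exp(-5 x 0.2554) = 9.4, or 7.2 with dropout

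*Close at 80 events.* Solving for the time T at which expected events in both arms reach 80, the number enrolled more than 5 years before T is 135 x (T - 5)/4.
- HR 0.50, no dropout: T = 5.2 years, 7.0 enrolled early enough, 3.7 still event-free at 5 years
- HR 0.50, with dropout: T = 5.6 years, 20.1 enrolled early enough, 8.2 still event-free and in follow-up
- No drug effect: T = 4.2 to 4.3 years, so none

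All these counts assume that no one stops drug for other reasons.

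**4. The denominator.**
The documents give no figure for participants who never complete a test. Assume 10-20%. A true 10% rate among those tested, divided by everyone treated, reads as 10% x 0.90 = 9% to 10% x 0.80 = 8%.

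**The case against.** The strongest reply is that the gap is narrow and the stated risk is low. The 5 mg/kg/day figure is a ceiling, and rounding down to 100 mg steps puts most weights below it. Section 7.2 gives an upper bound of 2% over 10 years and notes that retinopathy found by sensitive methods is not the same as clinically significant visual loss. Section 7.3 itself adds that withdrawal from therapy at the endpoint shortens exposure. All of this stands, and it limits the point to the accuracy of one sentence. It does not rescue that sentence: falling slightly under the ceiling still leaves participants within 4-5 mg/kg/day, and withdrawal at the endpoint shortens exposure only for those who progress.

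A reader might infer several stronger things that the documents do not support.
- *That continuing on drug without a completed test contradicts the dose or duration figures.* It does not. The screening recommendation cited in 7.2 starts annual examination only after 5 years at this dose. The conflict is with the annual-examination texts.
- *That such participants are unmonitored, or that the retinal rules cannot be triggered for them.* Section 4.5.1 (dose withholding, item 3) refers to any abnormal ophthalmologic finding and 4.5.2 item 3 to clinically significant retinal change; neither is limited to OCT or visual fields. A fundus photograph or examination is attempted at baseline.
- *That those affected are mostly very young children.* Section 7.3 mentions them only as an example.
- *That 2.7 retinopathy cases should be expected (2% of 135).* That applies a 10-year upper bound to a mean exposure of about 2.8 to 3.1 years under the same assumptions.

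**Conclusion.** The point holds as an inaccurate assurance. The 7.3 dose sentence does not agree with 7.2, which gives a risk for the band containing the target, or with 2.2.3, whose reassurance needs both a dose strictly below 5 mg/kg/day and less than 5 years of therapy. Sections 2.2.3 and 7.2 also differ from each other on whether the time limit applies.

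The number of active participants who pass the 5-year limit depends on how the trial closes: 4-8 at 80 events or 14-18 at 6 years if the hazard ratio is 0.50, and 0 or 7-9 with no drug effect. The upper figures therefore need both the assumed benefit and a full 6-year close.

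The examination texts are in real tension: two places say that examinations will occur and one says that they will be attempted. The effect on any reported rate is proportional to the fraction never tested, which is unknown; the 8-9% reading rests on an assumed 10-20%. None of this shows that participants are harmed or that the dose is wrong.

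**What to change.** 1. Correct the 7.3 sentence so that it agrees with the risk figures in 2.2.3 and 7.2, and align those two sections on the 5-year condition. Check that the consent text agrees; it was not available for this review.
2. Reconcile Protocol 2.2.3, 4.5.1 (dose withholding, item 3), 4.5.2 item 3, 7.3 and Appendix 2 note 7 on participants without a completed retinal test. How to do so is for the sponsor and the DSMB; no dose, stopping or hold rule is proposed here.
3. In the SAP safety tables and the DSMB reports, add by arm the number of participants with no completed post-baseline retinal test, and the retinal-finding rate among those tested, next to the rate on the total population.

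The cost is a wording amendment and one extra table, with no new procedures. The downside is a slightly less favourable risk statement.
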